
1.3 Research Design and Methods

This is a randomized trial conducted by the Rutgers Cancer Institute of New Jersey and at NJMS/University Hospital Newark), which will prospectively enroll 160 patients with proven SARS-CoV-2 infection by qPCR assay with symptoms consistent with COVID-19 such as a fever of ≥ 100.6. This study will evaluate the efficacy of Azithromycin and Hydroxychloroquine in this patient population. Study participants will be randomized to 1) Azithromycin and Hydroxychloroquine; 2) Hydroxychloroquine alone; or 3) placebo for 6 days followed by hydroxychloroquine. Treatment with the investigational agents will continue for 10 days. Viral loads will be collected to monitor response to treatment at baseline and on day 3 and day 6.

A. Research Procedures

1. Study Procedures:

- Day 0 Screening Visit:
 - Obtain informed consent for trial enrollment
 - Demographic data
 - Medical history
 - Physical examination
 - Vital signs (blood pressure, heart rate, temperature)
 - Document disease severity (mild, moderate or severe)
 - Severity Assessment Criteria
 - Temp >100.5°F (1 point)
 - Fatigue (1 point)
 - Cough (1 point)
 - Shortness of breath (1 point)
 - Heart rate >90 BPM (2 points)
 - Respiratory rate > 14 breathes/min (2 points)
 - Pulse Ox < 94% on room air (3 points)
 - Blood pressure < 90/60 (3 points)

Score:

Mild/Moderate = 0-7 points

Severe = 8-15 points

- o Document location of patient (inpatient versus outpatient)
- Review eligibility criteria
- o Complete baseline COVID signs and symptoms questionnaire (Appendix C)
- Electrocardiogram. The QT corrected interval may be calculated by either Bazett's, Fridericia's, or Framingham's formula.
 - Bazett's formula: QTc = QT/ √(RR in seconds)
 - Fridericia's formula: QTc = QT/RR^0.33)
 - Framingham's formula: QTc = QT + 0.154 (1-RR)
- Labs: CBCD, Ferritin, D-Dimer, LDH, CRP and Troponin (8 mL); urine or serum pregnancy test for women of childbearing potential
- Concomitant medications (starting from the time the patient signs the informed consent)
- Collect research specimens: saliva, oropharynx swab and whole blood (16 mL)
- Randomize study participant through OnCore®
- Dispense study medication
- Provide education to patient on how to complete pill diary and temperature log.
 Each subject will receive an electric thermometer for use.
- Treatment Period For those study participants randomized to Arm 1 and Arm 2:
 - o Days 1 10

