 - Study participant doses self with prescribed study medications (unless inpatient)
 - Assessment completed by Research Nurse. May be conducted by phone.
 - Complete follow-up COVID signs and symptoms questionnaire (Appendix D)
 - Review of daily temperatures
 - Review of medication compliance

- Record standard of care treatments and/or procedures prescribed
- Day3 or 4 and Day 6

Repeat physical examination

- Labs: CBCD, Ferritin, D-Dimer, LDH, CRP and Troponin (8 mL) (Day 6 only)
- Collect research specimens: saliva, oropharynx swab and whole blood (16 mL)
- Day 10 (+/- 1 day)
 - Repeat physical examination
 - Labs: CBCD, Ferritin, D-Dimer, LDH, CRP and Troponin (8 mL)
- o Day 11-20 Daily Follow-up
 - Assessment completed by Research Nurse. May be conducted by phone.
 - Review of symptoms
 - Review of daily temperatures
 - Adverse events
 - Record standard of care treatments and/or procedures prescribed
- Treatment Period For those study participants randomized to Arm 3:
 - o Days 1 5
 - Study participant doses self with prescribed study medications (placebo), unless inpatient.
 - Assessment completed by Research Nurse. May be conducted by phone.
 - Complete follow-up COVID signs and symptoms questionnaire (Appendix D)
 - Review of daily temperatures
 - Review of medication compliance
 - Adverse events
 - Record standard of care treatments and/or procedures prescribed
 - Day3 or 4 and Day 6
 - Repeat physical examination
 - Labs: CBCD, Ferritin, D-Dimer, LDH, CRP and Troponin (8 mL) (Day 6 only)
 - Collect research specimens: saliva, oropharynx swab and whole blood (16 mL)
 - If patient continues to have symptoms of COVID-19 on Day 6, will initiate Hydroxychloroquine sulfate for home administration.
 - o Day 10
 - Repeat physical examination
 - Labs: CBCD, Ferritin, D-Dimer, LDH, CRP and Troponin (8 mL)
 - o Day 11-15
 - Study participant doses self with prescribed study medications (unless inpatient)
 - Assessment completed by Research Nurse. May be conducted by phone.
 - Complete follow-up COVID signs and symptoms questionnaire (Appendix D)
 - Review of daily temperatures

Confirmed COVID-19

Protocol Version Date: 08-May-2020

OI

- Adverse events
- Record standard of care treatments and/or procedures prescribed

Day 15-20 - Daily Follow-up

- Assessment completed by Research Nurse. May be conducted by phone.
- Review of symptoms
- Review of daily temperatures
- Adverse events
- Record standard of care treatments and/or procedures prescribed

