1.7 Drugs/Devices/Biologics

Generic name: Azithromycin

Commercial name: Zithromax, Zmax

For complete information please refer to the package inserts at https://dailymed.nlm.nih.gov/dailymed/azithromycin

 $\frac{\text{Chemical name:}}{\alpha\text{-L-ribo-hexopyranosyl}} (2R,3S,4R,5R,8R,10R,11R,12S,13S,14R) - 13-[(2,6-dideoxy-3-C-methyl-3-O-methyl-3-C-$

Azithromycin Tablets USP contain the active ingredient azithromycin, USP, a macrolide antibacterial drug, for oral administration. Azithromycin, USP is derived from erythromycin; however, it differs chemically from erythromycin in that a methyl-substituted nitrogen atom is incorporated into the lactone ring.

Source: Commercially available

C38H72N2O12 M.W. 749

Azithromycin, USP, as the monohydrate, is a white crystalline powder with a molecular formula of C38H72N2O12•H2O and a molecular weight of 767. Azithromycin Tablets USP are supplied for oral administration as tablets containing azithromycin monohydrate equivalent to either 250 mg or 500 mg azithromycin, USP.

Pharmacokinetics: Following oral administration of a single 500 mg dose (two 250 mg tablets) to 36 fasted healthy male volunteers, the mean (SD) pharmacokinetic parameters were AUC0-72 = 4.3 (1.2) mcg·hr/mL; Cmax= 0.5 (0.2) mcg/mL; Tmax = 2.2 (0.9) hours. Two azithromycin 250 mg tablets are bioequivalent to a single 500 mg tablet. Elimination: Plasma concentrations of azithromycin following single 500 mg oral and IV doses declined in a polyphasic pattern resulting in a mean apparent plasma clearance of 630 mL/min and terminal elimination half-life of 68 hr. The prolonged terminal half-life is thought to be due to extensive uptake and subsequent release of drug from tissues. Biliary excretion of azithromycin, predominantly as unchanged drug, is a major route of elimination. Over the course of a week, approximately 6% of the administered dose appears as unchanged drug in urine. The mean Cmax and AUC0-120 increased 61% and 35%, respectively, in subjects with severe renal impairment (GFR < 10 mL/min) compared to subjects with normal renal function (GFR > 80 mL/min).

Contraindications:

sensitivity: Azithromycin tablets are contraindicated in patients with known hypersensitivity to azithromycin, erythromycin, any macrolide or ketolide drug.

Hepatic Dysfunction: Azithromycin tablets are contraindicated in patients with a history of cholestatic jaundice/hepatic dysfunction associated with prior use of azithromycin.

Warnings:

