Hypersensitivity: Serious allergic reactions, including angioedema, anaphylaxis, and dermatologic reactions including Acute Generalized Exanthematous Pustulosis (AGEP), Stevens-Johnson syndrome, and toxic epidermal necrolysis have been reported in patients on azithromycin therapy. Fatalities have been reported. Cases of Drug Reaction with Eosinophilia and Systemic Symptoms (DRESS) have also been reported. If an allergic reaction occurs, the drug should be discontinued and appropriate therapy should be instituted. Physicians should be aware that allergic symptoms may reappear when symptomatic therapy has been discontinued.

Hepatotoxicity: Abnormal liver function, hepatitis, cholestatic jaundice, hepatic necrosis, and hepatic failure have been reported, some of which have resulted in death. Contact their physician if vomiting or irritability with feeding occurs.

QT Prolongation: Prolonged cardiac repolarization and QT interval, imparting a risk of developing cardiac arrhythmia and torsades de pointes, have been seen with treatment with macrolides, including azithromycin. Cases of torsades de pointes have been spontaneously reported during post marketing surveillance in patients receiving azithromycin. Providers should consider the risk of QT prolongation which can be fatal when weighing the risks and benefits of azithromycin for at-risk groups including:

 patients with known prolongation of the QT interval, a history of torsades de pointes, congenital long QT syndrome, bradyarrhythmia's or uncompensated heart failure

patients on drugs known to prolong the QT interval

 patients with ongoing proarrhythmic conditions such as uncorrected hypokalemia or hypomagnesemia, clinically significant bradycardia, and in patients receiving Class IA (quinidine, procainamide) or Class III (dofetilide, amiodarone, sotalol) antiarrhythmic agents.

Elderly patients may be more susceptible to drug-associated effects on the QT interval.

Clostridium difficile-Associated Diarrhea (CDAD): Clostridium difficile-associated diarrhea has been reported with use of nearly all antibacterial agents, including azithromycin, and may range in severity from mild diarrhea to fatal colitis. Treatment with antibacterial agents alters the normal flora of the colon, leading to overgrowth of C. difficile.

Exacerbation of Myasthenia Gravis: Exacerbation of symptoms of myasthenia gravis and new onset of myasthenic syndrome have been reported in patients receiving azithromycin therapy.

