Ocular: Irreversible retinal damage has been observed in some patients who had received hydroxychloroquine sulfate. Significant risk factors for retinal damage include daily doses of hydroxychloroquine sulfate greater than 6.5 mg/kg (5 mg/kg base) of actual body weight, durations of use greater than five years, subnormal glomerular filtration, use of some concomitant drug products such as tamoxifen citrate and concurrent macular disease.

Cardiac Effects, including Cardiomyopathy and QT prolongation: Post-marketing cases of life-threatening and fatal cardiomyopathy have been reported with use of hydroxychloroquine sulfate as well as with use of chloroquine. Hydroxychloroquine sulfate prolongs the QT interval. Ventricular arrhythmias and torsades de pointes have been reported in patients taking hydroxychloroquine sulfate (see OVERDOSAGE). Therefore, hydroxychloroquine sulfate should not be administered with other drugs that have the potential to prolong the QT interval.

Worsening of psoriasis and porphyria

Proximal Myopathy and Neuropathy

Neuropsychiatric events, including suicidality

Hypoglycemia: Hydroxychloroquine sulfate has been shown to cause severe hypoglycemia including loss of consciousness that could be life threatening in patients treated with or without antidiabetic medications

General precautions: General: Use with caution in patients with gastrointestinal, neurological, or blood disorders, and in those with a sensitivity to quinine.

Hepatic/Renal Disease: Antimalarial compounds should be used with caution in patients with hepatic disease or alcoholism or in conjunction with known hepatotoxic drugs. A reduction in dosage may be necessary in patients with hepatic or renal disease, as well as in those taking medicines known to affect these organs.

Hematologic Effects/Laboratory Tests: Antimalarial compounds should be used with caution in patients with hepatic disease or alcoholism or in conjunction with known hepatotoxic drugs. Periodic blood cell counts should be performed if patients are given prolonged therapy.

Hydroxychloroquine sulfate should be administered with caution in patients having glucose-6-phosphate dehydrogenase (G-6-PD) deficiency.

Dermatologic Effects: Dermatologic reactions to hydroxychloroquine sulfate may occur and, therefore, proper care should be exercised when it is administered to any patient receiving a drug with a significant tendency to produce dermatitis.

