- Short Form Consent for Non-English Speakers
 Study participants who do not speak English will be presented with a short form consent document written in a language understandable to them.
- D. Adults Unable to Consent / Decisionally Impaired Adults Patients that lack decision-making capacity will not be approached to participate in this study. N/A
- 4.6 Economic Burden and/or Compensation for Subjects
 - A. Expenses
 - B. Compensation/incentives
 Study participants will not receive compensation for participation.
 - C. Compensation Documentation N/A
- 4.7 Risks of Harm/Potential for Benefits to Subjects
 - A. Description of Risks of Harm to Subjects
 - Reasonably Foreseeable Risks of Harm

Azithromycin Adverse Events:

The incidence from three different regimens all based on the five (5) dosing regimen planned, is described in the table below (Pfizer package labeling).

Dosage Regimen	Diarrhea %	Abdominal Pain %	Vomiting %	Nausea %	Rasi
5-day	1.8%	1.2%	1.1%	0.5%	0.4%
Dosage Regimen	Diarrhea/Loose stools %	Abdominal Pain %	Vomiting %	Nausea %	Rash %
5-day	5.8%	1.9%	1.9%	1.9%	1.6%
Dosage Regimen	Diarrhea %	Abdominal Pain %	Vomiting %	Nausea %	Rash %
5-day	5.4%	3.4%	5.6%	1.8%	0.7%

- · Cardiovascular: Palpitations, chest pain.
- Gastrointestinal: Dyspepsia, flatulence, vomiting, melena, and cholestatic jaundice.
- Genitourinary: Monilia, vaginitis, and nephritis.
- Nervous System: Dizziness, headache, vertigo, and somnolence.
- General: Fatigue.
- Allergic: Rash, pruritus, photosensitivity, and angioedema.
- Laboratory Abnormalities: Clinically significant abnormalities (irrespective of drug relationship) occurring during the clinical trials were reported as follows: with an incidence of greater than 1%: decreased hemoglobin, hematocrit, lymphocytes, neutrophils, and

blood glucose; elevated serum creatinine phosphokinase, potassium, ALT, GGT, AST, BUN, creatinine, blood glucose, platelet count, lymphocytes, neutrophils, and eosinophils; with an incidence of less than 1%: leukopenia, neutropenia, decreased sodium, potassium, platelet count, elevated monocytes, basophils, bicarbonate, serum alkaline phosphatase, bilirubin, LDH, and phosphate. Most subjects with elevated serum creatinine also had abnormal values at baseline. When follow-up was provided, changes in laboratory tests appeared to be reversible.

Hydroxychloroquine Sulfate Adverse Events:

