vision disturbances, or photophobia. They may be transient or are reversible upon discontinuation of therapy (see Warnings and Precautions, Ophthalmologic). Not known: Macular degeneration, which may be irreversible.

Gastrointestinal disorders

Very common: ≥ 10 %: Abdominal pain, nausea.

Common: Diarrhea, vomiting.

These symptoms usually resolve immediately upon reducing the dose or upon stopping the treatment.

Hepatobiliary disorders

Uncommon: ≥ 0.1 and < 1 %: Abnormal liver function tests.

Not known: Fulminant hepatic failure (see Warnings and Precautions, Hepatic/Biliary/Pancreatic).

Immune system disorders

Not known: Urticaria, angioedema, bronchospasm.

Metabolism and nutrition disorders

Common: ≥ 1 and <10 %: Anorexia (usually resolves immediately upon reducing the dose or upon stopping the treatment).

Not known: hypoglycemia (see Warnings and Precautions, Endocrine and Metabolism). Hydroxychloroquine may exacerbate porphyria (see Warnings and Precautions, General).

Musculoskeletal and connective tissue disorders

Uncommon: ≥ 0.1 and < 1 %: Sensori motor disorders.

Not known: Skeletal muscle palsies or skeletal muscle myopathy or neuromyopathy leading to progressive weakness and atrophy of proximal muscle groups. Depression of tendon reflexes, abnormal results of nerve conduction tests. Myopathy may be reversible after drug discontinuation, but recovery may take many months (see Warnings and Precautions, Musculoskeletal).

Nervous system disorders

Common: ≥ 1 and <10 %: Headache.

Uncommon: Dizziness.

Not known: Convulsions. Extrapyramidal reactions such as: akathisia, dystonia, dyskinesia, gait disturbance, tremor.

Psychiatric disorders

Common: ≥ 1 and <10 %: Affect lability. Uncommon: ≥ 0.1 and < 1 %: Nervousness. Not known: Psychosis, suicidal behavior.

Skin and subcutaneous tissue disorders

Common: ≥ 1 and <10 %: Skin rash, pruritus.

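### No required lab test measures potassium or magnesium before Arm 1 starts two QT-prolonging drugs, although the protocol names low values of either as a QT risk for azithromycin

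*Protocol*

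**What the plan says.** **Required labs.** The Day 0 list in Protocol section 1.3 A.1 reads "Labs: CBCD, Ferritin, D-Dimer, LDH, CRP and Troponin (8 mL); urine or serum pregnancy test for women of childbearing potential". The same six blood tests are required on Days 6 and 10 in every arm. The flow table in Appendix A repeats them at screening, Day 6 and Day 10.

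**Risk named by the protocol.** The azithromycin warnings in section 1.7 state: "Providers should consider the risk of QT prolongation which can be fatal when weighing the risks and benefits of azithromycin for at-risk groups". One of the groups then listed is "patients with ongoing proarrhythmic conditions such as uncorrected hypokalemia or hypomagnesemia, clinically significant bradycardia". For the partner drug the same section says: "Hydroxychloroquine sulfate prolongs the QT interval". It also advises against giving HCQ with other drugs that can prolong QT. Appendix B puts both drugs in its known-risk column.

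**Exposure.** Under section 1.3 A.2, Arm 1 takes HCQ for 10 days with azithromycin on Days 1 to 5. For Arm 3, section 1.3 A.1 says: "If patient continues to have symptoms of COVID-19 on Day 6, will initiate Hydroxychloroquine sulfate for home administration".

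**QT safeguards.** An ECG is scheduled at screening only. Section 4.1 C excludes patients with a QTc of 470 msec or more, long QT syndrome, a family history of sudden death, earlier drug-induced prolongation, current QT-prolonging drugs, or specified ventricular arrhythmias.

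**The concern.** Arm 1 combines two drugs that the protocol itself says prolong QT. A low potassium or magnesium value is one of the few listed risk states that a blood test can find and that can be corrected before dosing. Section 1.7 asks the provider to weigh this risk, but the trial procedures do not ensure that the provider has the two values. Section 4.1 C turns several other QT risks into exclusions and leaves this one out.

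What is at stake is patient safety rather than the primary analysis. The outcome concerned is an arrhythmia that the protocol describes as possibly fatal. Outpatients dose themselves, and many of their assessments may be made by phone, so for them routine chemistry is least assured.

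**Working it through.** The finding rests on comparing texts. The arithmetic only sets its scale, and the plan gives no figure of its own on this point to reproduce.

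**Step 1. Where a potassium or magnesium test could appear**

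| Place | Content | Potassium or magnesium? |
|---|---|---|
| Section 1.3 A.1, Day 0 | CBCD, ferritin, D-dimer, LDH, CRP, troponin, pregnancy test | No |
| Section 1.3 A.1, Days 6 and 10 | The same six blood tests | No |
| Appendix A, flow table | The same six tests; no chemistry row | No |
| Section 1.8, research blood | Viral load, cytokines, serology | No |
| Section 4.1 C, eligibility | QTc, QT history, QT drugs, arrhythmia | Not named |
| Section 1.3 A.2, dose modification | Toxicity grades for HCQ | Not named |

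So 0 of 3 required lab time points measure either electrolyte, and no visible criterion or dosing rule names one. The procedure list, flow table and eligibility list agree with each other.

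**Step 2. Whether another safeguard requires the test**

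- The screening ECG and the exclusions address QT risk directly at entry, but they do not measure electrolytes.
- Routine-care labs (section 1.1 A and SAP section 6.4 A) are used if obtained. They are not mandated, and the examples in section 1.1 A include no electrolytes.
- The Appendix D questionnaire asks about new vomiting and diarrhea, daily during treatment. A positive answer could prompt a test but does not require one.
- The grade 3 or 4 HCQ rule could apply to a severe disturbance once recognised. No required test would reveal it.

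**Step 3. Scale**

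Inputs: 160 patients and 2:2:1 randomization (SAP section 6.1); azithromycin label rates (section 4.7 A).

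- Arm 1: 160 × 2/5 = 64 patients, 40% of the trial. Arm 3: 160 × 1/5 = 32.
- Diarrhea, 1.8% to 5.8%: 0.018 × 64 = 1.2 to 0.058 × 64 = 3.7 patients.
- Vomiting, 1.1% to 5.6%: 0.011 × 64 = 0.7 to 0.056 × 64 = 3.6 patients.
- Decreased potassium, below 1% ("with an incidence of less than 1%: leukopenia, neutropenia, decreased sodium, potassium, platelet count"): fewer than 0.01 × 64 = 0.64 patients.

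These rates come from other azithromycin populations and are given irrespective of drug relationship. The same paragraph lists raised potassium at above 1%, so it does not show that potassium tends to fall. None of these figures gives the frequency of low values at entry to this trial. The documents give neither that frequency nor the inpatient/outpatient split.

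**The case against.** The best reply is that QT risk is already screened directly by an ECG, a QTc limit and several exclusions, that daily symptom review covers gastrointestinal loss, and that section 1.7 reproduces label guidance asking providers to consider risk. It does not prescribe a test. All of this is true and narrows the gap. It does not close it, because each of these safeguards can operate exactly as written while potassium and magnesium remain unknown.

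Parts of section 4.7 (items C to E) are also not visible, so the finding is limited to the visible text. The places where a required test would normally be stated can be read.

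Four stronger readings are tempting, and the documents do not support them:

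- **That HCQ alone carries the same electrolyte warning.** The wording on low potassium and magnesium occurs only under azithromycin. The HCQ cardiac warning names no electrolyte. For Arms 2 and 3 the case rests only on HCQ's QT effect and on its gastrointestinal effects ("Common: Diarrhea, vomiting").
- **That a Day 6 test is as necessary as a Day 0 test.** The last azithromycin dose is on Day 5, so a Day 6 result cannot change azithromycin dosing.
- **That the share of azithromycin left after Day 5 can be computed.** Section 1.7 gives a "terminal elimination half-life of 68 hr" but describes the decline as polyphasic after single doses. Applying the terminal half-life from the end of dosing would overstate plasma levels.
- **That creatinine should be added as well.** The documents show no benefit from that over a 10-day course.

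**Conclusion.** The concern holds for the Day 0 check. Followed as written, the plan can start an Arm 1 patient on two QT-prolonging drugs with neither potassium nor magnesium measured, although the protocol names low values of either as a risk state for one of those drugs. About 64 of 160 patients are allocated to that combination. The gap falls mainly on those treated as outpatients without routine chemistry.

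The number who would have a low value cannot be stated. On the label figures, a fall in potassium during azithromycin treatment is uncommon, but the harm could be fatal and the cause can be corrected. That justifies an inexpensive change. A reader might infer that the plan leaves QT risk unmanaged or breaks an instruction of its own. It does neither: QT risk is screened in several ways, and section 1.7 calls for judgement rather than a test.

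The conclusion assumes that the sections that cannot be read contain no electrolyte requirement and that routine care does not always supply one.

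**What to change.** **Recommended.** Add potassium and magnesium to the existing Day 0 draw. Review both before randomization, so that any delay is unrelated to arm, and at the latest before the first dose. Correct any value below the laboratory's lower limit before dosing starts. State the rule in section 1.3 A.1, section 4.1 C and Appendix A.

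**Optional.** Repeat both assays on the existing Day 6 draw in all arms under the same rule, so that the review does not reveal allocation. The reason is that HCQ continues to Day 10 in Arms 1 and 2 and symptomatic Arm 3 patients start it on Day 6. A short wait then leaves the primary endpoint untouched, because Arm 3 starts HCQ after the Day 6 viral sample.

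**Cost.** Two routine assays per draw and a short amendment. The documents do not show that the 8 mL draw covers chemistry, so one extra tube may be needed. Waiting for results may prevent same-day dosing where screening and Day 1 are combined, as note 4 of Appendix A allows, and a few starts may be delayed while low values are corrected.

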1.10 Timetable/Schedule of Events

Please refer to Appendix A. All study procedures will be performed according to the schedule outlined in the Study Flow Table

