Appendix A – Study Flow Table

Procedures	Screening Day 0 ⁴	D1	D2	D3	D4	D5	D6	D7	D8	D9	D10	D11-D20	Weekly FUP x 4 ²	Monthly FUP x 6 ³
Informed consent	X													
Baseline Medical History	X													
Physical assessment	X			X			x				x			
Demographics	X													
Electrocardiogram	X													
CBCD, CRP, Ferritin, D-Dimer, LDH and Troponin	X						x				x			
Serum pregnancy (if applicable)	X													
Eligibility Review	X													
Randomization	X													
Study Drug Dispensing	X						X ¹							
Azithromycin (Arm 1)		X	X	X	X	X								
Hydroxychloroquine sulfate (Arm 1 & 2)		X	X	X	X	X	X	X	X	X	X			
Placebo/ Hydroxychloroquine sulfate (Arm 3) ¹		X	X	X	X	X	X	X	X	X	X	X		
Research Blood draw	X			X			X							
Saliva, Oropharynx swabs	X			X			X							
Pill Diary Review	X	X	X	X	X	X	X	X	X	X	X	X		
Daily Temperature Review	X	X	X	X	X	X	X	X	X	X	X	X	X	X
Adverse Event Review		X	X	X	X	X	X	X	X	X	X	X	X	X
Concomitant Medication Review	X	X	X	X	X	X	X	X	X	X	X	X		
COVID-19 Symptom Questionnaire	X	X	X	X	X	X	X	X	X	X	X	X	X	X
Record other SOC Procedures	X	X	X	X	X	X	X	X	X	X	X	X	X	X

1. Treatment will be administered Day 6 to D15 for Arm 3.
2. Phone assessments - weekly x 4 weeks (+/- one day).
3. Phone assessments – monthly x 6 months (+/- one week).
4. Screening and Day 1 visits may be combined. All procedures may be completed within 24 hours of screening visit.

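### Protocol Section 1.3 and Appendix A disagree on whether Arm 3 has daily symptom, temperature and adverse-event review on Days 6–10; a site following Section 1.3 would record Arm 3 symptom resolution late.

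*Protocol*

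**What the plan says.** Protocol Section 1.3 sets out two arm-specific visit lists. The one headed "Treatment Period For those study participants randomized to Arm 1 and Arm 2" has a research-nurse assessment on each of Days 1–10, with the Appendix D questionnaire and a review of daily temperatures. The one headed "Treatment Period For those study participants randomized to Arm 3" has the same contact on Days 1–5, the block whose dosing line reads "Study participant doses self with prescribed study medications (placebo), unless inpatient". It then lists Day 6 (examination, laboratory tests, specimens) and Day 10 (examination, laboratory tests), and resumes daily contacts on Days 11–15. The Day 6 entry includes a symptom-based step: "If patient continues to have symptoms of COVID-19 on Day 6, will initiate Hydroxychloroquine sulfate for home administration".

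Section 1.10 says "All study procedures will be performed according to the schedule outlined in the Study Flow Table". That table, Appendix A in the SAP document, marks the rows "COVID-19 Symptom Questionnaire" and "Daily Temperature Review", and the adverse-event row, in every column from D1 to D10 and in D11–D20. Only its drug rows separate the arms.

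SAP Section 6.1 (Other analyses) and Protocol Section 1.5 plan Kaplan-Meier curves and log-rank tests for time to symptom resolution, assessed by questionnaire, and for time to being afebrile for 48 hours. Protocol Section 1.3 F labels the secondary endpoints descriptive.

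**The concern.** A time-to-event comparison is fair only if the event is looked for equally often in each arm. On the Section 1.3 lists, an Arm 2 patient whose symptoms resolve on Day 7 is recorded on Day 7. An Arm 3 patient with the same course is not asked again until Day 11. Appendix D asks only about the last day, so the Day 11 form does not recover the earlier date. Arm 3 would look slower with no drug effect at all.

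Section 1.3 is the only arm-by-arm visit instruction, and nothing in it warns that its Arm 3 list is shorter than the flow table. The days at issue also include the first days on which Arm 3 may take hydroxychloroquine.

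**Working it through.** **Step 1: the schedules side by side.** Inputs are the two Section 1.3 lists and Appendix A.

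| Days | Section 1.3, Arms 1 and 2 | Section 1.3, Arm 3 | Appendix A, all arms |
|---|---|---|---|
| 1–5 | Nurse contact, Appendix D, temperatures | Same | Questionnaire, temperatures, AEs |
| 6 | As above, plus examination, labs, specimens | Examination, labs, specimens, symptom-based decision | Same as Days 1–5 |
| 7–9 | Nurse contact, Appendix D, temperatures | Nothing listed | Same as Days 1–5 |
| 10 | As above, plus examination, labs | Examination, labs | Same as Days 1–5 |
| 11–15 | Nurse contact, symptom review without Appendix D, temperatures | Nurse contact, Appendix D, temperatures | Same as Days 1–5 |

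Days within Days 1–10 with a listed questionnaire and temperature review: Section 1.3 gives 10 of 10 in Arms 1 and 2 and 5 of 10 in Arm 3; Appendix A gives 10 of 10 in every arm. The Section 1.3 gap is 10 − 5 = 5 days, of which three (Days 7–9) have no entry of any kind. On Days 11–15 the difference reverses, with Appendix D listed for Arm 3 only.

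**Step 2: the delay for one patient.** If a resolution on Day d (6 to 10) is first recorded on Day 11, the delay is 11 − d, which is 5 days at most and 1 day at least.

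**Step 3: the share of patients exposed.** The documents give no distribution for time to resolution, so this is an assumption. With exponential times and median m, the share resolving on Days 6–10 is 2^(−5/m) − 2^(−10/m). At m = 6 this is 0.561 − 0.315 = 0.246; at m = 12 it is 0.749 − 0.561 = 0.188. With gamma times of shape 3 the share is about 44% at m = 6 and 28% at m = 12.

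**Step 4: effect on the log-rank test.** The plan states no figure to reproduce. Arm sizes are from SAP Section 6.1: 60 in Arm 2 and 30 in Arm 3. Assumptions: the same true distribution in both arms, whole-day times, censoring at Day 20. On each day, e events occur among n patients at risk, with e₁ and n₁ in Arm 2. Then U = Σ(e₁ − e·n₁/n), V = Σ e(n₁/n)(1 − n₁/n)(n − e)/(n − 1), and the test rejects if U²/V > 3.841. Rejection rates under no effect:

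| Time distribution | Arm 3 events recorded late | Median 6 | 8 | 10 | 12 days |
|---|---|---|---|---|---|
| Exponential | Days 6–10 moved to Day 11 | 8% | 6% | 5% | 5% |
| Gamma, shape 2 | Days 6–10 moved to Day 11 | 23% | 11% | 8% | 6% |
| Gamma, shape 3 | Days 6–10 moved to Day 11 | 47% | 23% | 10% | 6% |
| Gamma, shape 3 | Days 7–9 moved to Day 10 | 13% | 7% | 4% | 5% |
| Any, no gap (Appendix A followed) | None | about 5% at every median | | | |

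Each cell rests on 1,500 to 4,000 runs. At a true 5% and 1,500 runs the standard error is √(0.05 × 0.95/1,500) = 0.0056, so entries of 4–6% cannot be told apart from 5%. For shape 3 with the full shift and medians of 6–10 days, almost all rejections favour the hydroxychloroquine arm.

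**The case against.** The strongest reply is that Section 1.10 makes Appendix A the schedule to follow, and under Appendix A there is no gap. Section 1.3 also cannot be an exhaustive list: read that way, Arm 3 has no dosing entry between Day 5 and Day 11, contrary to the Treatment Plan and the Appendix A footnote. The omission therefore looks like a drafting slip. This stands, and it defeats the stronger reading that the endpoints **are** observed differently by arm. They would be only where a site works from Section 1.3.

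Other inferences a reader might draw also go too far:

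- **The fever endpoint is biased in the same way.** Section 1.3 C requires temperatures four times a day with no limit by arm, and patients keep a log. A Day 7 reading reviewed on Day 11 still belongs to Day 7, so this endpoint is largely protected.
- **Arm 3 has weaker adverse-event review than Arms 1 and 2.** The available text of the Arms 1 and 2 Days 1–10 list has no adverse-event line either (it may have been lost at a page break), and Section 1.3 C requires collection throughout treatment.
- **The false-positive rate is 47%.** That is the extreme corner: shape 3, median 6 days, and nothing learned at the Day 6 or Day 10 visit. Day 6 already involves a judgement about continuing symptoms, and Day 10 is an examination.
- **The contact schedule breaks the blind.** Appendix A already has Arm 3-specific dispensing on Day 6, so a different call pattern afterwards adds little.

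The endpoint is also labelled descriptive, the SAP names no arm pair for these log-rank tests, and symptomatic Arm 3 patients may start hydroxychloroquine from Day 6, so the contrast is not a clean one. These points limit the consequence. They do not remove the contradiction, and a descriptive curve would be distorted by late recording too.

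**Conclusion.** The concern holds as an internal contradiction with a conditional risk of bias. Section 1.3 lists the questionnaire and temperature review on 5 of Arm 3's first 10 days, against 10 of 10 in Arms 1 and 2, while Appendix A lists them on all 10 for everyone. That mismatch is certain from the text.

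The bias arises only at sites following Section 1.3, and it bears on time to symptom resolution in Arm 2 versus Arm 3, in the direction of the hydroxychloroquine arm. For medians of 6–12 days, log-rank rejection under no effect is about 5–8% (exponential), 6–23% (gamma shape 2) or 6–47% (gamma shape 3) with the full Day 6–10 shift. It is about 4–13% under shape 3 if only Days 7–9 are missed and picked up on Day 10. The documents support no particular shape or median, so no single figure should be quoted. The Day 6 viral primary endpoint is not touched. The point deserves correction because the remedy is nearly free.

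**What to change.** Replace the assessment entries in the two arm-specific lists of Section 1.3 with one list for all arms that matches Appendix A: daily contact on Days 1–20 with the Appendix D questionnaire, temperature review and adverse-event review. This also removes the reverse difference on Days 11–15. Keep only study-drug dispensing and dosing entries arm-specific.

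The Arm 3 dosing days must also be reconciled across the Section 1.3 visit list (dosing entries on Days 1–5 and 11–15), the Treatment Plan (placebo on Days 1–6, then hydroxychloroquine for 10 days after Day 6 sampling) and the Appendix A footnote (treatment Day 6 to Day 15). Day 15 also falls in two Arm 3 blocks of the visit list. Which entry is right is for the sponsor to settle.

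The cost is a wording change plus, at any site that had been following Section 1.3, up to five phone contacts per Arm 3 patient. With 30 such patients that is at most 5 × 30 = 150 contacts, all of them already scheduled in Appendix A.
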